## Listings

Output #	Population Title	Output Title
16.2.1.1	All Subjects	Informed Consent and Screen Failures
16.2.1.2	All Subjects	Subject Randomization, Site, and Country
16.2.1.3	Safety	Planned and Actual Treatment Assignments for Subjects with Incorrect Treatment, Part 1
16.2.1.3.ES	Safety	Planned and Actual Treatment Assignments for Subjects with Incorrect Treatment, Entire Study
16.2.1.4	ITT	Subject Disposition
16.2.1.5	All Subjects	Confirmation of Clinical Diagnosis of HAE
16.2.1.6	ITT	Analysis Populations
16.2.1.7	ITT	Subgroups Based on Baseline Characteristics
16.2.2.2	ITT	Protocol Deviations, Part 1
16.2.2.2.ES	ITT	Protocol Deviations Occurring During Part 2 of the Study
16.2.2.3	Safety	Subjects for Whom the Treatment Blind Was Broken, Part 1
16.2.2.3.ES	Safety	Subjects for Whom the Treatment Blind Was Broken, Entire Study
16.2.4.1	ITT	Inclusion/Exclusion Criteria Not Met
16.2.4.2.1	All Subjects	Demography
16.2.4.2.2	All Subjects	Demography - Contraception
16.2.4.3.1	ITT	Medical History
16.2.4.3.2	ITT	HAE Baseline Characteristics – HAE Medical History
16.2.4.3.3	Safety	HAE Medication History: Past and Current On-Demand HAE Treatment
16.2.4.3.4	Safety	HAE Medication History: Past Prophylactic HAE Treatment
16.2.4.4.1	Safety	Medications Discontinued Within 30 Days of Screening
16.2.4.4.2	Safety	Concomitant Medication Use, Part 1
16.2.4.4.2.ES	Safety	Concomitant Medication Use, Entire Study
16.2.4.4.3	Safety	Use of Concomitant Medications for HAE, Part 1
16.2.4.4.3.ES	Safety	Use of Concomitant Medications for HAE, Entire Study
16.2.4.5	ITT	Pre-Treatment Investigator-Confirmed Attack Rates and Angioedema Symptoms
16.2.5.1	Safety	Drug Accountability, Part 1
16.2.5.1.ES	Safety	Drug Accountability, Entire Study
16.2.5.2	Safety	Dosing Diary, Part 1
16.2.5.2.ES	Safety	Dosing Diary, Entire Study
16.2.5.3	Safety	Person-Years of Exposure, Part 1
16.2.5.3.ES	Safety	Person-Years of Exposure, Entire Study
16.2.6.1.1	ITT	HAE Attack Diary and Investigator Confirmation for All Attacks, Part 1
16.2.6.1.1.ES	ITT	HAE Attack Diary and Investigator Confirmation dor All Attacks, Entire Study

Output #	Population Title	Output Title
16.2.6.1.2	ITT	HAE Attack Diary and Investigator Confirmation (Investigator-Confirmed Attacks Only), Part 1
16.2.6.1.2.ES	ITT	HAE Attack Diary and Investigator Confirmation (Investigator-Confirmed Confirmed Attacks Only), Entire Study
16.2.6.1.3	ITT	HAE Attack Diary Detail - Subject-Reported Attacks, Part 1
16.2.6.1.3.ES	ITT	HAE Attack Diary Detail - Subject-Reported Attacks, Entire Study
16.2.6.1.4	ITT	HAE Attack Diary Detail - Investigator-Confirmed Attacks, Part 1
16.2.6.1.4.ES	ITT	HAE Attack Diary Detail - Investigator-Confirmed Attacks, Entire Study
16.2.6.1.5	ITT	HAE Attack Level Summary - Subject-Reported Attacks, Part 1
16.2.6.1.5.ES	ITT	HAE Attack Level Summary - Subject-Reported Attacks, Entire Study
16.2.6.1.6	ITT	HAE Attack Level Summary - Investigator-Confirmed Attacks, Part 1
16.2.6.1.6.ES	ITT	HAE Attack Level Summary - Investigator-Confirmed Attacks, Entire Study
16.2.6.1.7	ITT	Attack Rate, Part 1
16.2.6.1.7.ES	ITT	Attack Rate, Entire Study
16.2.6.1.8	ITT	Imputed Investigator-Confirmed Attack Rates for Subjects with Missing Data, Part 1
16.2.6.1.9	ITT	Subjects Who Are Investigator-Confirmed Attack-Free During Entire Dosing Period and Effective Dosing Period, Part 1
16.2.6.1.9.ES	ITT	Subjects Who Are Investigator-Confirmed Attack-Free During Entire Dosing Period and Effective Dosing Period, Entire Study
16.2.6.1.10	ITT	Days with Angioedema Symptoms from Investigator-Confirmed Attacks, Part 1
16.2.6.1.10.ES	ITT	Days with Angioedema Symptoms from Investigator-Confirmed Attacks, Entire Study
16.2.6.1.11.1	ITT	Subject-Level Efficacy Endpoint Profile, Part 1
16.2.6.1.11.2	ITT	Subject-Level Additional Derived Endpoint Profile, Part 1
16.2.6.2.1	ITT	AE-QoL: Individual Question Responses and Days Missed, Part 1
16.2.6.2.1.ES	ITT	AE-QoL: Individual Question Responses and Days Missed, Entire Study
16.2.6.2.2	ITT	AE-QoL: Domain Scores, Part 1
16.2.6.2.2.ES	ITT	AE-QoL: Domain Scores, Entire Study
16.2.6.3.1	ITT	TSQM Global Satisfaction Individual Responses, Part 1
16.2.6.3.1.ES	ITT	TSQM Global Satisfaction Individual Responses, Entire Study
16.2.6.3.2	ITT	TSQM Effect, Side Effect, Convenience and Global Satisfaction Scores, Part 1
16.2.6.3.2.ES	ITT	TSQM Effect, Side Effect, Convenience and Global Satisfaction Scores, Entire Study
16.2.6.4.1	ITT	EQ-5D-5L Individual Question Responses, Part 1
16.2.6.4.1.ES	ITT	EQ-5D-5L Individual Question Responses, Entire Study
16.2.6.4.2	ITT	EQ-5D-5L Descriptive, VAS, and Index Scores, Part 1
16.2.6.4.3	ITT	EQ-5D-5L for Usual Attack Individual Question Responses, Part 1
16.2.6.4.3.ES	ITT	EQ-5D-5L for Usual Attack Individual Question Responses, Entire Study
16.2.6.4.4	ITT	EQ-5D-5L for Usual Attack Descriptive, VAS, and Index Scores, Part 1
16.2.6.4.4.ES	ITT	EQ-5D-5L for Usual Attack Descriptive, VAS, and Index Scores, Entire Study
16.2.6.5.1	ITT	WPAI Individual Question Responses, Part 1
16.2.6.5.1.ES	ITT	WPAI Individual Question Responses, Entire Study
16.2.6.5.2	ITT	WPAI Absenteeism, Presenteeism, Word Productivity Loss, and Activity Impairment Scores, Part 1

Output #	Population Title	Output Title		
16.2.6.5.2.ES	ITT	WPAI Absenteeism, Presenteeism, Word Productivity Loss, and Activity Impairment Scores, Entire Study		
16.2.7.1	Safety	Adverse Events, Part 1		
16.2.7.1.ES	Safety	Adverse Events, Entire Study		
16.2.7.2	Safety	Serious Adverse Events, Part 1		
16.2.7.2.ES	Safety	Serious Adverse Events, Entire Study		
16.2.7.3	Safety	Grade 3 or 4 Adverse Events, Part 1		
16.2.7.3.ES	Safety	Grade 3 or 4 Adverse Events, Entire Study		
16.2.7.4	Safety	Adverse Events Leading to Permanent Discontinuation of Study Drug, Part 1		
16.2.7.4.ES	Safety	Adverse Events Leading to Permanent Discontinuation of Study Drug, Entire Study		
16.2.7.5.1	Safety	Fatal Serious Adverse Events, Part 1		
16.2.7.5.2	Safety	Fatal Serious Adverse Events, Entire Study		
16.2.7.6	Safety	Adverse Events Leading to Interruption of Study Drug, Part 1		
16.2.7.6.ES	Safety	Adverse Events Leading to Interruption of Study Drug, Entire Study		
16.2.7.7	Safety	Investigator-identified Rash, Part 1		
16.2.7.7.ES	Safety	Investigator-identified Rash, Entire Study		
16.2.7.8	Safety	GI Abdominal-Related Adverse Events, Part 1		
16.2.7.8.ES	Safety	GI Abdominal-Related Adverse Events, Entire Study		
16.2.7.9	Safety	Adverse Events For Subjects with Elevated LFTs, Part 1		
16.2.7.9.ES	Safety	Adverse Events For Subjects with Elevated LFTs, Entire Study		
16.2.7.10	ITT	Listing of GI Abdominal-Related Adverse Events and Unconfirmed HAE Attacks with Abdominal-Only Symptoms, Part 1		
16.2.7.10.ES	ITT	Listing of GI Abdominal-Related Adverse Events and Unconfirmed HAE Attacks with Abdominal-Only Symptoms, Entire Study		
16.2.8.1	Safety	Clinical Chemistry, Part 1		
16.2.8.1.ES	Safety	Clinical Chemistry, Entire Study		
16.2.8.2	Safety	Hematology, Part 1		
16.2.8.2.ES	Safety	Hematology, Entire Study		
16.2.8.3	Safety	Coagulation, Part 1		
16.2.8.3.ES	Safety	Coagulation, Entire Study		
16.2.8.4	Safety	Urinalysis, Part 1		
16.2.8.4.ES	Safety	Urinalysis, Entire Study		
16.2.8.5	Safety	Other Laboratory Tests, Part 1		
16.2.8.5.ES	Safety	Other Laboratory Tests, Entire Study		
16.2.8.6	Safety	Complement Factors C3, C4, and C1-INH, Part 1		
16.2.8.6.ES	Safety	Complement Factors C3, C4, and C1-INH, Entire Study		
16.2.8.7	ITT	SERPING Results		
16.2.8.8	ITT	Pregnancy Tests, Part 1		
16.2.8.8.ES	ITT	Pregnancy Tests, Entire Study		
16.2.8.9	Safety	Laboratory Abnormalities, Part 1		

Output #	Population Title	Output Title	
16.2.8.9.ES	Safety	Laboratory Abnormalities, Entire Study	
16.2.8.10	Safety	Grade 3 or Grade 4 Laboratory Abnormalities, Part 1	
16.2.8.10.ES	Safety	Grade 3 or Grade 4 Laboratory Abnormalities, Entire Study	
16.2.8.11	Safety	All Liver Function Test Results for Subject Experiencing a Treatment-Emergent Grade 3 or 4 Liver Function Test, Part 1	
16.2.8.11.ES	Safety	All Liver Function Test Results for Subject Experiencing a Treatment-Emergent Grade 3 or 4 Liver Function Test, Entire Study	
16.2.8.12	Safety - Subjects with Prior Androgen Use	All Liver Function Test Results for Subject Experiencing a Treatment-Emergent Grade 3 or 4 Liver Function Test, Part 1	
16.2.8.12.ES	Safety - Subjects with Prior Androgen Use	All Liver Function Test Results for Subject Experiencing a Treatment-Emergent Grade 3 or 4 Liver Function Test, Entire Study	
16.2.8.13	Safety	Vital Signs, Part 1	
16.2.8.13.ES	Safety	Vital Signs, Part 1, Entire Study	
16.2.8.14	Safety	12-Lead Electrocardiogram, Part 1	
16.2.8.14.ES	Safety	12-Lead Electrocardiogram, Entire Study	
16.2.8.15	Safety	QTcF Values > 450 msec or QTF Change from Baseline Values > 30 msec, Part 1	
16.2.8.15.ES	Safety	QTcF Values > 450 msec or QTF Change from Baseline Values > 30 msec, Entire Study	
16.2.8.16	Safety	Physical Exam, Part 1	
16.2.8.16.ES	Safety	Physical Exam, Entire Study	
16.2.8.17	Safety	Pharmacokinetic Sample Collection, Part 1	
16.2.8.17.ES	Safety	Pharmacokinetic Sample Collection, Entire Study	
16.2.8.18	PD	Plasma Kallikrein Inhibition (%), Part 1	
16.2.8.18.ES	PD	Plasma Kallikrein Inhibition (%), Entire Study	

#### Figures

Output #	Population Title	Output Title
14.1.1.2	All Subjects	CONSORT Diagram, Part 1
14.1.1.2.ES	All Subjects	CONSORT Diagram, Entire Study
14.1.5.2	Safety	Plot of Duration of Exposure to Study Drug, Part 1
14.1.5.2.ES	Safety	Plot of Duration of Exposure to Study Drug, Entire Study
14.2.1.7	ITT	Box Plot of Individual Investigator-Confirmed Attack Rate for Entire Dosing Period, Part 1
14.2.1.7.ES	ITT	Box Plot of Individual Investigator-Confirmed Attack Rate for Entire Dosing Period, Entire Study
14.2.1.8	ITT	Cumuative Distribution Plot of Individual Investigator-Confirmed Attack Rate for Entire Dosing Period, Part 1
14.2.1.8.ES	ITT	Cumulative Distribution Plot of Individual Investigator-Confirmed Attack Rate for Entire Dosing Period, Entire Study
14.2.1.9	ITT	Forest Plot of Results of Sensitivity Analyses of Investigator-Confirmed Attack Rate for Entire Dosing Period, Part 1
14.2.1.10	ITT	Forest Plot of Results of Subgroup Analyses of Investigator-Confirmed Attack Rate for Entire Dosing Period, Part 1

Output #	Population Title	Output Title		
14.2.1.12	ITT	Box Plot of Individual Investigator-Confirmed Attack Rate for Effective Dosing Period, Part 1,		
14.2.1.12.ES	ITT	Box Plot of Individual Investigator-Confirmed Attack Rate for Effective Dosing Period, Entire Study		
14.2.1.13	ITT	Cumulative Distribution Plot of Individual Investigator-Confirmed Attack Rate for Effective Dosing Period, Part 1		
14.2.1.13.ES	ITT	Cumulative Distribution Plot of Individual Investigator-Confirmed Attack Rate for Effective Dosing Period, Entire Study		
14.2.2.2	ITT	Histogram Plot of Baseline Investigator-Confirmed Attack Rate, Part 1		
14.2.2.3	ITT	Plot of Mean Investigator-Confirmed Attack Rate by Month, Part 1		
14.2.2.3.ES	ITT	Plot of Mean Investigator-Confirmed Attack Rate by Month, Entire Study		
14.2.2.3.P3	ITT	Plot of Mean Subject-Reported Attack Rate by Month, Part 3		
14.2.2.4	ITT	Plot of On-Study Investigator-Confirmed Attack Rate vs Baseline Investigator-Confirmed Attack Rate, Part 1		
14.2.2.4.ES	ITT	Plot of On-Study Investigator-Confirmed Attack Rate vs Baseline Investigator-Confirmed Attack Rate, Entire Study		
14.2.2.5	ITT	Plot of Difference Between On-Study Investigator-Confirmed Attack Rate and Baseline Investigator-Confirmed Attack Rate vs Baseline Investigator-Confirmed Attack Rate, Part 1		
14.2.2.6	ITT	Plot of Change from Baseline Attack Rate Versus Percent Compliance, Part 1		
14.2.3.3	ITT	Plot of Mean AE-QoL Scores Over Time, Part 1		
14.2.3.3.ES	ITT	Plot of Mean AE-QoL Scores Over Time, Entire Study		
14.2.3.4	ITT	Plot of Mean Change from Baseline AE-QoL Scores Over Time, Part 1		
14.2.3.4.ES	ITT	Plot of Mean Change from Baseline AE-QoL Scores Over Time, Entire Study		
14.2.3.5	ITT	Cumulative Distribution of Total AE-QoL Change from Baseline at Week 24		
14.2.3.6	ITT	Forest Plot of Results of Subgroup Analyses of Total AE-QOL Change from Baseline at Week 24, Part 1		
14.2.8.2	ITT	Kaplan-Meier Plot of Time to First Investigator-Confirmed Attack, Part 1		
14.2.9.2	ITT	Kaplan-Meier Plot of Time to First Use of Targeted HAE Rescue Medication to Treat an Investigator-Confirmed Attack, Part 1		
14.3.1.13	ITT	Forest Plot of Treatment-Emergent Adverse Events Sorted by Relative Risk, Part 1		
14.3.1.13.ES	ITT	Forest Plot of Treatment-Emergent Adverse Events Sorted by Relative Risk, Entire Study		
14.3.1.26	Safety	Kaplan-Meier Plot of Time to Development of Investigator-identified Rash, Part 1		
14.3.1.26.ES	Safety	Kaplan-Meier Plot of Time to Development of Investigator-identified Rash, Entire Study		
14.3.1.28	Safety	Kaplan-Meier Plot of Duration of Investigator-identified Rash, Part 1		
14.3.1.28.ES	Safety	Kaplan-Meier Plot of Duration of Investigator-identified Rash, Entire Study		
14.3.1.40	Safety	Kaplan-Meier Plot of Time to First Occurrence of a GI Abdominal-related Adverse Event Part 1		
14.3.1.40.ES	Safety	Kaplan-Meier Plot of Time to First Occurrence of a GI Abdominal-related Adverse Event Entire Study		
14.3.1.42	Safety	Kaplan-Meier Plot of Duration of GI Abdominal-related Adverse Events Part 1		
14.3.1.42.ES	Safety	Kaplan-Meier Plot of Duration of GI Abdominal-related Adverse Events Entire Study		
14.3.1.43	Safety	Plot of Occurrence of Treatment-Emergent GI Abdominal-related Adverse Events, Part 1		
14.3.1.43.ES	Safety	Plot of Occurrence of Treatment-Emergent GI Abdominal-related Adverse Events, Entire Study		
14.3.5.20	Safety	Plot of Liver Function Test Profiles for Subjects with Grade 3 or 4 Liver Abnormalities, Part 1		
14.3.5.21	Safety	Hy's Law Plot of Maximum Total Bilirubin vs. Maximum ALT, Part 1		

Output #	Population Title	Output Title		
14.3.5.21.ES	Safety	Hy's Law Plot of Maximum Total Bilirubin vs. Maximum ALT, Entire Study		
14.3.5.22	Safety	Liver Test Safety Panel Over Time, Baseline vs. On-Study, Part 1		
14.3.5.22.ES	Safety	Liver Test Safety Panel Over Time, Baseline vs. On-Study, Entire Study		
14.3.5.23	Safety	Distribution of Liver Tests Over Time: ALT, AST, ALP, and Bilirubin, Part 1		
14.3.5.23.ES	Safety	Distribution of Liver Tests Over Time: ALT, AST, ALP, and Bilirubin, Entire Study		
14.3.5.24	Safety	Distribution of Cholesterol and Triglycerides Over Time, Part 1		
14.3.5.24.ES	Safety	Distribution of Cholesterol and Triglycerides Over Time, Entire Study		
14.3.5.26	Safety	Kaplan-Meier Plot of Time to First Occurrence of Grade 3 or 4 ALT Part 1		
14.3.5.28	Safety	Kaplan-Meier Plot of Time to First Occurrence of Grade 3 or 4 AST Part 1		
14.3.5.30	Safety	Kaplan-Meier Plot of Time to First Occurrence of Grade 3 or 4 Total Bilirubin, Part 1		
14.3.6.2	Safety	Distribution of Diastolic and Systolic Blood Pressure Over Time, Part 1		
14.3.6.2.ES	Safety	Distribution of Diastolic and Systolic Blood Pressure Over Time, Entire Study		
14.3.7.4	Safety	Distribution of QTcF Over Time, Part 1		
14.3.7.4.ES	Safety	Distribution of QTcF Over Time, Entire Study		
14.4.1.2	ITT	Plot of Mean WPAI Scores Over Time, Part 1		
14.4.1.2.ES	ITT	Plot of Mean WPAI Scores Over Time, Entire Study		
14.4.1.3	ITT	Plot of Mean Change from Baseline WPAI Scores Over Time, Part 1		
14.4.1.3.ES	ITT	Plot of Mean Change from Baseline WPAI Scores Over Time, Entire Study		
14.4.2.2	ITT	Plot of Mean EQ-5D-5L VAS Scores Over Time, Part 1		
14.4.2.2.ES	ITT	Plot of Mean EQ-5D-5L VAS Scores Over Time, Entire Study		
14.4.2.3	ITT	Plot of Mean Change from Baseline EQ-5D-5L VAS Scores Over Time, Part 1		
14.4.2.3.ES	ITT	Plot of Mean Change from Baseline EQ-5D-5L VAS Scores Over Time, Entire Study		
14.4.2.5	ITT	Plot of Mean EQ-5D-5L VAS Scores from Usual Attack Over Time, Part 1		
14.4.2.5.ES	ITT	Plot of Mean EQ-5D-5L VAS Scores from Usual Attack Over Time, Entire Study		
14.4.2.6	ITT	Plot of Mean Change from Baseline EQ-5D-5L VAS Scores from Usual Attack Over Time, Part 1		
14.4.2.6.ES	ITT	Plot of Mean Change from Baseline EQ-5D-5L VAS Scores Usual Attack Over Time, Entire Study		
14.4.2.8	ITT	Plot of Mean Change from Baseline EQ-5D-5L Index Scores Over Time, Part 1		
14.4.2.8.ES	ITT	Plot of Mean Change from Baseline EQ-5D-5L Index Scores Over Time, Entire Study		
14.4.2.9	ITT	Plot of Mean Change from Baseline EQ-5D-5L Index Scores Over Time, Part 1		
14.4.2.9.ES	ITT	Plot of Mean Change from Baseline EQ-5D-5L Index Scores Over Time, Entire Study		
14.4.2.11	ITT	Plot of Mean EQ-5D-5L Index Scores from Usual Attack Over Time, Part 1		
14.4.2.11.ES	ITT	Plot of Mean EQ-5D-5L Index Scores from Usual Attack Over Time, Entire Study		
14.4.2.12	ITT	Plot of Mean Change from Baseline EQ-5D-5L Index Scores from Usual Attack Over Time, Part 1		
14.4.2.12.ES	ITT	Plot of Mean Change from Baseline EQ-5D-5L Index Scores Usual Attack Over Time, Entire Study		
14.4.3.2	ITT	Plot of Mean TSQM Scores Over Time, Part 1		
14.4.3.2.ES	ITT	Plot of Mean TSQM Scores Over Time, Entire Study		
14.4.3.3	ITT	Plot of Mean Change from Baseline TSQM Scores Over Time, Part 1		

Output #	Population Title	Output Title	
14.4.3.3.ES	ITT	Plot of Mean Change from Baseline TSQM Scores Over Time, Entire Study	
14.6.1.2	PK-PD	Scatterplot of Kallekrein Inhibition (%) and BCX7353 Plasma Concentration/4by Study Visit, Part 1	
14.6.1.2.ES	PK-PD	Scatterplot of Kallekrein Inhibition (%) and BCX7353 Plasma Concentration/4by Study Visit, Entire Study	

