#### Test product, dose and mode of administration:

BCX7353 capsules, to be administered orally.

BCX7353 capsules contain 55 and 75 mg of the active ingredient (free base equivalents). Subjects will take the following orally QD at approximately the same time each day, with whichever meal is typically the largest of the day:

Treatment Group 1 (110 mg QD) Parts 1 and 2: two 55-mg capsules of BCX7353 Treatment Group 2 (150 mg QD) Parts 1 and 2: two 75-mg capsules of BCX7353

Subjects randomized to Treatment Group 1 or 2 will receive the same dose in both Parts 1 and 2, for a total duration of 48 weeks of treatment during Parts 1 and 2 (24 weeks of treatment in each study part for Parts 1 and 2).

Subjects randomized to Treatment Group 3 (placebo) in Part 1 will be re-randomized to receive active study drug from the Week 24 visit (Part 2):

Treatment Group 3a (110 mg QD) Part 2: two 55-mg capsules of BCX7353

Treatment Group 3b (150 mg QD) Part 2: two 75-mg capsules of BCX7353

#### Part 3

BCX7353 capsules contain 110 and 150 mg of the active ingredient (free base equivalents). Subjects will take a single capsule orally once daily at approximately the same time each day, with whichever meal is typically the largest of the day.

Treatment Groups 1 and 3a (110 mg QD) Part 3: one 110-mg capsule of BCX7353

Treatment Groups 2 and 3b (150 mg QD) Part 3: one 150-mg capsule of BCX7353

Subjects randomized to Treatment Groups 1 and 2 will receive a total of up to 96 weeks of active BCX7353 treatment. Subjects randomized to Treatment Group 3 will receive a total of up to 72 weeks of active BCX7353 treatment.

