Demographic and baseline characteristic displays will be repeated for Part 2 to characterize the subset of subjects who continue in Part 2. Total columns will be included. For these displays the treatment descriptors will be as shown in Table 6. The descriptors shown in Table 6 also apply to any displays specific to Part 3.

Sort order	Treatment Descriptor	Notes
1	110 mg	110 mg
2	150 mg	150 mg
3	110 mg after placebo	For subjects who were originally randomized to placebo and were randomized to 110 mg for Parts 2 with continuation of treatment in Part 3.
4	150 mg after placebo	For subjects who were originally randomized to placebo and were randomized to 150 mg for Parts 2 with continuation of treatment in Part 3.

Table 6:Treatment Descriptors for Displays using only Part 2 or Part 3

For tables that cover the entire study period, 110 and 150 mg data from subjects assigned to placebo in Part 1 will be separated from 110 and 150 mg data from subjects assigned to active treatment in Part 1. For some tables, there will also be columns that combine data from each active treatment whether received in Part 2 and 3 only or during the entire study. Treatment descriptors are provided in Table 7.

Sort order	Treatment Descriptor	Notes
1	110 mg	110 mg (originally randomized)
2	110 mg after placebo	Active treatment data from subjects who were originally randomized to placebo and were randomized to 110 mg for Parts 2 and 3
3	All 110 mg	Combines 110 mg data from subjects originally assigned to placebo with 110 mg data from subjects originally assigned to 110 mg
4	150 mg	150 mg (originally randomized)
5	150 mg after placebo	Active treatment data from subjects who were originally randomized to placebo and were randomized to 150 mg for Parts 2 and 3
6	All 150 mg	Combines 150 mg data from subjects originally assigned to placebo with 150 mg data from subjects originally assigned to 150 mg
7	All active	Combines all data collected for 110 and 150 mg treatment regardless of original randomization of subject
8	Placebo	Placebo (includes data from Part 1 only)

 Table 7:
 Treatment Descriptors for Displays for Entire Study

Note: Not all columns will be required for any given table.

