### 10.1.1. Summaries of Adverse Event Incidence Rates for All Subjects and Incidence Rates for Serious Adverse Events, Discontinuations due to Adverse Events, and Deaths

A brief summary of TEAEs will show, by treatment group, the number and percentage of subjects who 1) had any TEAE, 2) had any drug-related event, 3) permanently discontinued from study drug due to an TEAE, 4) had any serious adverse event (SAE), 5) had any Grade 3 or higher TEAE, 6) had any Grade 3 or higher drug-related TEAE, 7) had any TEAE leading to interruption of study drug, 8) had a drug-related SAE, or 9) had a fatal SAE.

TEAEs will be summarized by treatment group. For each SOC and PT, the number and percentage of subjects reporting an event will be calculated. In summary tables, SOCs and events within a SOC will be presented by decreasing frequency count based on the total number of events. Multiple events (by subject or SOC as appropriate) will be counted only once per subject per dose in each summary. For summaries that use severity grade, the most severe event will be selected.

The following summary tables (number and percentage of subjects) of TEAEs (by SOC and PT) will be provided by treatment group:

- Overall summary of TEAEs
- Summary of TEAEs
- Summary of drug-related TEAEs
- Summary of TEAEs by severity
- Summary of treatment-emergent Grade 3 or Grade 4 AEs
- Summary of drug-related, treatment-emergent Grade 3 or Grade 4 AEs

### 70

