# CONFIDENTIAL

- Summary of TESAEs
- Summary of TEAEs leading to permanent discontinuation of study treatment
- Summary of TEAEs leading to interruption of study treatment
- Summary of drug-related TESAEs

In addition, a summary of frequent TEAEs will be provided by PT (not by SOC and PT), in decreasing order of frequency. Frequent TEAEs will be defined as events that occur in at least 5% of the total number of subjects in the clinical trial.

A summary of TEAEs by age group will also be provided

Data listings will be provided for all AE data. In addition to listing all AEs, distinct data listings will also be provided for the following:

- Grade 3 or Grade 4 AEs
- AEs leading to permanent study discontinuation
- SAEs (fatal and non-fatal)

A forest plot of most-frequent treatment-emergent AEs sorted by relative risk will be produced using the format recommended by the FDA/Industry/Academia Safety Graphics working group (https://www.ctspedia.org/do/view/CTSpedia/StatGraphHome). The format of the plot to be used is the example plot of most-frequent on-therapy AEs sorted by risk difference. However, the relative risk (aka risk ratio) will be displayed rather than the risk difference. The 95% confidence interval for the relative risk will be derived using the assumption of normality of the log of the relative risk.

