### 10.1.4. Summaries of Adverse Event Incidence Rates per 100 Person-Years of Exposure to Study Treatment

For this study, the duration of exposure to study treatment will vary depending on whether the subject is initially assigned to placebo. Because of this, certain TEAE tables will be repeated using the number of TEAEs per 100 person-years of exposure instead of using a count, where 1 year = 365.25 days of exposure. These tables will not be created for the Part 1 primary efficacy analysis since the same amount of exposure is expected per treatment group for Part 1 analysis.

To determine the rate of TEAEs per person-year of exposure, the duration of treatment exposure will be computed for each subject and treatment. The rate of TEAEs per person-year will then
be calculated as the count of TEAEs divided by the duration of treatment exposure. This value will then be multiplied by 100 to compute the rate per 100 person-years of exposure. For subjects initially randomized to placebo, there will be exposure time for placebo treatment and a separate exposure time for treatment with either 110 or 150 mg. The total exposure for the treatment group of interest will sum the individual subject exposure time for each treatment group.

The following summary tables of rate of TEAEs per 100 person-years of exposure will be provided by treatment group (by SOC and PT):

- Summary of TEAE rate per 100 person-year of exposure
- Summary of drug-related, TEAE rate per 100 person-year of exposure
- Summary of TESAEs per 100 person-year of exposure

A listing of exposure to study treatment in 100 person-years will be provided by subject and treatment.

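### The entire-study adverse-event forest plot (Figure 14.3.1.13.ES) sets risks over up to 72 to 96 weeks on drug against 24 weeks on placebo, so its relative risks exceed 1 even for an inert drug

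*SAP*

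**What the plan says.** SAP 10.1.1 plans a forest plot of the most frequent TEAEs in which "the relative risk (aka risk ratio) will be displayed rather than the risk difference". On precision it says: "The 95% confidence interval for the relative risk will be derived using the assumption of normality of the log of the relative risk". It mentions neither an exposure term nor a limit on the time window. The tables in the same section count people: "the number and percentage of subjects reporting an event will be calculated", with repeat events in one person counted once per dose. The figure list in SAP 17.1 has the plot for Part 1 (14.3.1.13) and again as 14.3.1.13.ES, "Forest Plot of Treatment-Emergent Adverse Events Sorted by Relative Risk, Entire Study". Both are assigned to the ITT population, whereas the adverse-event tables use the safety population.

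Follow-up differs by design. For entire-study displays, SAP 6.1 (Table 7) describes the last column as "Placebo (includes data from Part 1 only", and placebo is given for 24 weeks. On the active side, the SAP summary states: "Subjects randomized to Treatment Groups 1 and 2 will receive a total of up to 96 weeks of active BCX7353 treatment". For Group 3, after placebo, the maximum is 72 weeks.

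SAP 10.1.4 recognises that "the duration of exposure to study treatment will vary depending on whether the subject is initially assigned to placebo". For that reason it repeats certain TEAE tables per 100 person-years for the entire study, and omits them for Part 1 because exposure there is expected to be equal. Three such TEAE tables are listed (14.3.1.45.ES to 14.3.1.47.ES), plus one for liver tests (14.3.5.31.ES). No exposure-adjusted forest plot is listed.

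The SAP does not say which columns the plot compares. A note to Table 7 says that not every column is needed in each table, and the shells are in a separate document. The SAP supplied is for Study BCX7353-302 and the protocol supplied is for BCX7353-202, so this point rests on the SAP alone.

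**The concern.** A relative risk is a fair drug-placebo comparison only if both groups are observed for the same time. Here one side may be followed three to four times as long as the other, and the measure is the proportion of people who ever had the event. That proportion can only rise with time, so the ratio moves above 1 without any drug effect. The printed interval would describe sampling error around an inflated value.

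The inflation also varies from row to row. It is largest for uncommon events and smaller for common ones, so a plot sorted by relative risk would rank events partly by their background frequency. A reader looking for the whole-study tolerability picture against placebo would go to this figure first.

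**Working it through.** **Plan's own figures.** Groups 1 and 2: 24 + 24 + 48 = 96 weeks on active. Group 3: 24 + 48 = 72 weeks on active. Placebo: 24 weeks. All agree with the SAP.

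**Group sizes.** The SAP plans about 40 subjects per group. The most that can receive active drug is 80 for 96 weeks plus 40 for 72 weeks, which is 120 subjects. Placebo has 40. Mean planned active follow-up is (80 × 96 + 40 × 72)/120 = 88 weeks.

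**Assumptions.** Placebo is the reference. The drug is inert, the hazard is constant and nobody drops out. The SAP gives no event rates, so the 24-week placebo risk p is shown as a range.

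**Formulas.**
- Risk by week T: 1 − (1 − p)^(T/24). Relative risk: that risk divided by p.
- Pooled active risk: (80 × risk at 96 weeks + 40 × risk at 72 weeks)/120.
- SE of log RR with a active and b placebo subjects having the event: √(1/a − 1/120 + 1/b − 1/40).

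**Example, p = 10%.** Risk at 72 weeks = 1 − 0.9³ = 0.271. Risk at 96 weeks = 1 − 0.9⁴ = 0.344. Pooled risk = (80 × 0.344 + 40 × 0.271)/120 = 0.320, so RR = 3.20. Expected counts are a = 38.4 and b = 4, giving SE = 0.49 and a CI of 1.22 to 8.39.

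| p | RR, 72 wk | RR, 96 wk | RR, pooled | CI at expected counts, 120 vs 40 |
|---|---|---|---|---|
| 5% | 2.85 | 3.71 | 3.42 | 0.84 to 13.98 |
| 7.5% | 2.78 | 3.57 | 3.31 | 1.07 to 10.26 |
| 10% | 2.71 | 3.44 | 3.20 | 1.22 to 8.39 |
| 20% | 2.44 | 2.95 | 2.78 | 1.47 to 5.28 |
| 30% | 2.19 | 2.53 | 2.42 | 1.49 to 3.93 |
| 50% | 1.75 | 1.88 | 1.83 | 1.34 to 2.51 |

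The CI column is what the SAP's method would print. It treats the 120 and the 40 as separate people, which is not so if ex-placebo subjects are in the active column.

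**Dropout, p = 10%.** Assume 20% discontinue per 24 weeks in every group (the SAP's sample-size section uses 20% overall). With event hazard h = −ln(0.9)/24 and dropout hazard d = −ln(0.8)/24, the observed risk is h/(h + d) × [1 − exp(−(h + d)T)]. The ratio to 24 weeks is 2.24 at 72 weeks and 2.61 at 96 weeks.

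**Early onset, p = 10%.** Suppose half of the 24-week cumulative hazard H = −ln(0.9) arises only soon after starting a treatment. Cumulative hazard is then H/2 + (H/2)(72/24) = 2H at 72 weeks and H/2 + (H/2)(96/24) = 2.5H at 96 weeks. RR = (1 − 0.9²)/0.1 = 1.90 and (1 − 0.9^2.5)/0.1 = 2.32.

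**After a fix.** With T = 24 on both sides, RR = p/p = 1. With a constant hazard, a rate ratio per person-year is h/h = 1.

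**The case against.** The strongest reply is that little depends on this figure. The SAP calls its safety analyses primarily descriptive, and no decision rule uses the plot. A Part 1 forest plot and Part 1 tables already give the equal-time comparison, and person-year tables cover the whole study. The bias also runs against the drug, so overall it would not hide harm. All of this stands, and it limits the consequence. It does not make the figure readable: the person-year tables report event rates and leave these subject-level ratios and their CIs uncorrected.

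Three stronger readings are tempting, and the documents do not support them.

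- **A relative risk of about 3 for every common event.** Each person is counted once, so the ratio saturates. The pooled value falls below 3 once the placebo risk passes about 15% and below 2 above about 44%. The weeks are also planned maxima.
- **A CI excluding 1 on nearly every row.** At p = 5% it runs from 0.84 to 13.98. The SAP calls an event frequent when at least 5% of all trial subjects have it. Over 96 weeks that corresponds to p = 1 − 0.95^(1/4) = 1.3%, or about 40 × 0.013 = 0.5 expected placebo subjects. Rows near that threshold would be uninformative.
- **Ex-placebo subjects certainly in both compared groups.** That depends on columns that the SAP leaves unnamed. If only originally randomised active subjects are used, the overlap disappears, but the contrast becomes 96 against 24 weeks (RR 3.44 at p = 10%).

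The objection that a person-year rate ratio has its own bias is also sound. If events cluster soon after starting treatment, an inert drug would give a rate ratio near 24/88 = 0.27, which could mask early harm.

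The ITT label is a small matter: undosed subjects add to the denominator but contribute no TEAEs.

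**Conclusion.** The concern holds. As specified, Figure 14.3.1.13.ES is an unadjusted risk ratio over unequal follow-up, and it is biased above 1. Under a constant hazard and no dropout, with placebo as the reference, an inert drug's expected pooled relative risk runs from about 3.4 (placebo risk 5%) through 3.2 (10%) and 2.4 (30%) to 1.8 (50%). Of the risks tabulated, 7.5% is the smallest at which the CI at expected counts excludes 1. Under the dropout and early-onset scenarios the ratio at 10% is about 1.9 to 2.6, still in the same direction.

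The placebo reference is an inference, though the natural one for this kind of plot. The event rates are assumptions. No efficacy conclusion is affected. What is at risk is a drug-versus-placebo safety figure with CIs that would mislead about both the size and the ordering of effects.

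**What to change.** Keep the Part 1 relative-risk plot (14.3.1.13) as the drug-versus-placebo comparison. For the entire study, choose one of these:

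1. Drop 14.3.1.13.ES.
2. Limit it to the first 24 weeks on each treatment.
3. Replace it with first-event incidence-rate ratios per 100 person-years with CIs, labelled as assuming a roughly constant hazard and read alongside the Part 1 plot.

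Use the safety population, as the adverse-event tables do, and name the compared columns in SAP 10.1.1. If the All 110 mg, All 150 mg or All active columns were set against placebo, ex-placebo subjects would be in both groups and the independent-groups CI would not apply. Compare placebo with originally randomised active subjects instead. With that restriction, option 2 largely reproduces the Part 1 plot, so option 1 loses little.

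The cost is a sentence or two in SAP 10.1.1, one output title and one program. No new data are needed.
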